8.8 Unblinding

Randomization data are kept strictly confidential, accessible only to authorized persons (in this case a member of the DCRI team and the pharmacists), until the time of unblinding. The investigative sites will be given access to the treatment code for their participants for emergency unblinding only by calling the CC. In the rare event of necessary unblinding, the CC Medical Monitor must be contacted to discuss the case. Any suspected study drug-related event should be treated as though the patient received active therapy.

At the end of the study, the assigned treatment arm will be unblinded and disclosed to subjects individually in order to allow subjects to seek further management of vestibulodynia with their gynecologist or primary care physician.

8.9 Concomitant Medication

All research participants are not allowed to consume other topical lidocaine, estradiol, or lidocaine/estradiol medications, TCAs, MAOIs, SSRIs, SNRIs, or opiates throughout the entire course of the study. This will be confirmed by the research team at the 8-, 16-, and 24-week visits. Study team will discuss concomitant medication use at the baseline screening visit.

9 RECRUITMENT, ENROLLMENT AND SCREENING PROCEDURES

9.1 Common Recruitment Procedures

Recruitment will occur via proven paths in clinics attended by members of the research team. At UNC this includes the Hillsborough Medical Office Building (HMOB) in both the Divisions of Minimally Invasive Gynecology (MIGS) and Female Pelvic Medicine and Reconstructive Pelvic Surgery (FPMRS) in the Department of Obstetrics and Gynecology (Ob/Gyn), which are located on the same floor in adjacent space. Participants will be recruited directly from the MIGS chronic pelvic and vulvar pain clinics and the FPMRS clinic. Patients may be contacted by phone prior to their scheduled appointment in the clinics above. In addition to the co-investigators, there are additional providers between the two clinical divisions who specialize in the care of women with pelvic and sexual pain, who will refer potential participants for the proposed study. Additionally, the Ob/Gyn generalist division, also located in the HMOB, will be a strong referral source. At UCLA, women will be recruited from the UCLA Chronic Pelvic Pain and Vulvar Pain Program, a clinical practice focused on the assessment and management of pelvic pain syndromes.

Women identified as new patients, with appointments in the upcoming weeks/months at the UCLA Chronic Pelvic Pain and Vulvar Pain clinic, may be contacted by phone or email prior to their scheduled appointment to determine their interest as a study participant. Women will also be referred from other generalists and specialists at UCLA Westwood, Santa Monica, and Los Angeles area as well as the UCLA Student Health and Wellness Ashe Center. In addition to this, many patients self-refer or maybe referred by their primary care physician or from outside medical groups.

Site PIs will conduct a weekly teleconference to review project-wide procedures, monitor targets, discuss operational or scientific processes, and address study-wide progress. Recruitment strategies include traditional recruitment methods. Study personnel will place flyers in surrounding institutions near UNC (Duke, NC State, Wake Tech, Durham Tech, Women's Health at UNC, Hillsborough, and Raleigh) and UCLA (University of Southern California, Santa Monica Community College, California State University- Northridge, Moorpark College, Pasadena Community College, and Pomona College). A mass email blast to all UNC and UCLA students and employees is scheduled for every 3 months to coincide with the start of each quarter. Transit advertising on public buses and radio advertisements through WUNC and KPCC National Public Radio (NPR) are options that may be used if necessary. Study information will be placed online on a study-specific website, on social media sites (eg, Instagram, Facebook, Twitter), on relevant University (eg, Duke List) and Association (eg, National Vulvodynia Association) sites, and through clinicaltrials.gov. . Another tool that will be utilized to target our audience will be Research Match, <https://www.researchmatch.org/>. We will list our study information on this website for more publicity.

In addition, we will perform data mining of CareConnect (Epic) using UCLA Clinical and Translation Science Institute (CTSI). We will provide CDWH with the ICD-9 or ICD-10 codes that identify our population, then provide filters (eg, age < 50, seen in last 5 years at UNC, live in NC). Once CDWH identifies the list of potential participants, we will contact them by phone or mail to evaluate their interest in participating in the study.

9.2 Estimated Enrollment Period

Each site will screen for eligible participants to achieve a target of 200 randomized participants per site. We expect to randomize an average of 4-5 participants per month per study site beginning in the second quarter of funding Year 2. At that rate, the final (400th) participant will be randomized at the end of Year 5. This projected rate of randomization is readily achievable based on current patient volume at UNC and UCLA (151 and 101 new patients per year, respectively), which is expected to increase with utilization of our recruitment methods.

9.3 Screening

Screening will be conducted in women aged 18-50 with VBD. The purpose of the study, study interventions and evaluations, and the potential risks and benefits of participation, will be explained to eligible participants. If a participant agrees to participate, she will review and sign the site-specific Institutional Review Board (IRB) approved informed consent form

10 BASELINE EVALUATION AND DRUG DISPENSING (0-WEEK)

Following screening, research participants will complete all baseline procedures, including 1) completion of validated questionnaires to measure perceived pain, health, mood, and sexual function 2) a vulvar exam and quantitative sensory testing to measure pressure pain thresholds at local and remote body sites, and 3) collection of biologic samples to measure local (vaginal)

and systemic (blood) cytokines and miRNAs. A complete schedule of assessments throughout the study is outlined in **Appendix A**.

10.1 Baseline Evaluation

Baseline procedures and assessments (described in detail in **Section 15** below) will be performed in the following order:

- Participant consent
- Tampon test with 0-10 NRS
- Blood collection and processing
- Participant questionnaires:
 - Demographics
 - Social history
 - Gynecological history
 - VPAQ
 - PROMIS BPSFS-F
 - COPC inventory
 - SF12v2
 - SCL-27
 - PILL
 - PSS
 - Sleep scale
- Remote bodily PPTs (deltoid, shin, trapezius)
- Qualitative pelvic sensory testing
- Vaginal sample collection
- Local vestibular PPTs (5, 6, and 7 o'clock)

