15.2 Analysis of the Aim 1 Endpoints

Primary endpoints will be the net change in vaginal vestibule pain following treatment measured using the Tampon Test and the Short-Form McGill Pain Questionnaire (SF-MPQ).

- The Tampon Test will provide a self-reported numeric rating scale of pain with self-tampon insertion, performed by the patient and reported to the research nurse. An Original Regular Tampax tampon will be inserted by the participant into her vagina and then she will be asked to verbally rate the pain on a scale of 0-10, with 0 meaning no pain and 10 meaning the worst possible pain. The Tampon Test has good reliability, construct validity, and responsiveness and is a recommended outcome measure for VBD clinical trials.⁹⁶
- The SF-MPQ measures perceived sensory qualities of pain using 11 descriptors and affective qualities related to pain using 5 descriptors. Responses on 4-point scales are summed to compute scores for each section.⁹⁷ SF-MPQ subscales have been successfully used to quantify treatment responses in trials for VBD and vulvodynia.⁹⁸⁻¹⁰⁰

Secondary endpoints include changes in pressure pain thresholds (PPTs) measured at the

- Vaginal Vestibule PPT will be determined using a digital vestibular algometer applied to 3 externally-accessed sites (2 and 10 o'clock on the upper vestibule and 6 o'clock on the lower vestibule) beginning at 1N and increasing until the participant's first sensation of pain or a maximum applied pressure of 10N.¹⁰²
- Levator Muscle Complex PPTs will be determined in a similar manner by applying the algometer internally to the right, midline, and left puborectalis levator muscles sites (5, 6, and 7 o'clock) just lateral to the perineum.
- Remote Bodily PPTs will be determined in a similar manner by applying the algometer to 3 'neutral' non-pelvic body sites (deltoid, shin, and trapezius), right and left, and calculating a composite score.

Data Analysis. The two primary statistical questions for Aim 1 are: 1a) Is peripheral treatment with lidocaine/estradiol compound cream, or central treatment with nortriptyline, or a combination of both treatments more effective for either VBD subtype than placebo? 1b) Is peripheral treatment more effective than central treatment in VBD-p, and is central treatment more effective than peripheral treatment in VBD-c?

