If the results for question 1a or 1b are statistically significant, the following primary outcomes will be analyzed using the same modeling strategies (models in 1a and 1b above): % decrease in pain score (tampon test) from baseline to the 16-week time point and % decrease in perceived pain on the SF-MPQ from baseline to the 16-week time point. Secondary outcomes include change in mucosal, vulvovaginal muscle, and remote bodily PPTs from baseline to the 16-week time point. Secondary outcomes also include change in pain scores and PPTs from baseline to the 8-week time point and change in pain scores and PPTs from the 16-week to the 24-week time point.

If the result for question 1b is non-significant, we will use the continuous COPC score in model 1b instead of a dichotomous VBD classification to compare treatment success for VBD-p and VBD-c. In addition, we use a binary treatment outcome (achievement of 30% pain reduction) to identify the optimal cutoff of the continuous COPC score in each treatment group.

Secondary analyses of muscle pain based on PPTs will also determine: a) the proportion of women with VBD that have a pelvic muscle pain component; b) differences in the distribution of muscle pain in VBD-p and VBD-c groups; and c) presence of muscle pain to predict treatment outcome. The latter will be tested by including the muscle pain variable (continuous or dichotomous) as part of the fixed effect term in model 1a.

Expected Outcomes. **1)** For women with VBD-p, peripheral lidocaine/estradiol treatment will be more effective than placebo or nortriptyline in reducing numeric pain ratings on the tampon test, perceived pain on the SF-MPQ, and pelvic PPTs on the algometer test at week 8 and week 16. **2)** For women with VBD-c, centrally-targeted nortriptyline treatment will be more effective than placebo or lidocaine/estradiol in reducing numeric pain ratings on the tampon test, perceived pain on the SF-MPQ, and pelvic/remote bodily PPTs on the algometer test at week 16. **3)** For women with VBD-c, combined peripheral and centrally-targeted treatments will be most effective in reducing pain on primary and secondary outcome measures at week 16. **4)** The two VBD subtypes will exhibit differential responses to treatment withdrawal at week 16, such that at the week 24 visit women with VBD-c will exhibit increases in pain after treatment withdrawal compared to women with VBD-p.

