20 APPENDICES

Appendix A. Schedule of Assessments

Assessment	Screening (0 week)	Baseline Visit (0 week)	Treatment Visit (8 week)*	Treatment Visit (16 week)**	Post-treatment (24 week)***
Patient Consent	X ^{FS}				
Tampon Test	X ^{FS}		X	X	X
Pain with sexual contact involving penetration into the vagina	X		X	X	X
Pain with touch to the vaginal opening	X		X	X	X
Blood Collection		X ^{FS}	X	X	X
Demographics		X ^{FS}			
Social History		X ^{FS}			
Gynecologic History		X ^{FS}			
VPAQ		X ^{FS}	X	X	X
PROMIS BPSFS-Female		X ^{FS}	X	X	X
COPC Inventory		X ^{FS}			
COPC Follow-Up			X	X	X
SF-12v2		X ^{FS}	X	X	X
SCL-27		X ^{FS}	X	X	X
PILL		X ^{FS}	X	X	X
PSS		X ^{FS}	X	X	X
Sleep Scale		X ^{FS}	X	X	X
Vaginal Sample Collection		X ^{FS}	X	X	X
Pelvic Sensory Testing		X ^{FS}	X	X	X
Vaginal Vestibule PPTs		X ^{FS}	X	X	X
Perineal Muscle PPTs		X ^{FS}	X	X	X
Levator Muscle PPTs		X ^{FS}	X	X	X
Remote Bodily PPTs		X ^{FS}	X	X	X
Medication Compliance			X	X	

FS = assessments collected for the feasibility study

[figure not shown]
X = assessments collected for the full study

*8 weeks (56 days) following randomization, +/- 5 days

**16 weeks (112 days) following randomization, +/- 5 days

***24 weeks (168 days) following randomization, +/- 5 days

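### The visit lists label the local PPT step vestibular but give it the clock positions that Section 15.2 assigns to the levator test, and they contain no levator step

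*Combined protocol and SAP*

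**What the plan says.** Sections 10.1, 11.1, 11.2 and 11.3 each set out the visit's procedures in a fixed order. All four end with the same line, "Local vestibular PPTs (5, 6, and 7 o'clock". It is the only local PPT step; the only other PPT step covers the remote body sites.

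Section 15.2 describes two different local tests. For the vestibule, the algometer is "applied to 3 externally-accessed sites (2 and 10 o'clock on the upper vestibule and 6 o'clock on the lower vestibule". The levator test is done by "applying the algometer internally to the right, midline, and left puborectalis levator muscles sites (5, 6, and 7 o'clock".

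Appendix A has four PPT rows: vestibule, "Perineal Muscle PPTs", levator and remote. Each is marked at baseline and at weeks 8, 16 and 24. The appendix gives no clock positions.

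Section 15.2 then analyses the tissues separately: "Secondary outcomes include change in mucosal, vulvovaginal muscle, and remote bodily PPTs from baseline to the 16-week time point". It adds three muscle-pain analyses: the share of women with a pelvic muscle component, how muscle pain is distributed between the subtypes, and whether it predicts treatment outcome.

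On direction, the first expected outcome in Section 15.2 describes effective treatment as "reducing numeric pain ratings on the tampon test, perceived pain on the SF-MPQ, and pelvic PPTs on the algometer test". Section 15.1 takes a higher PPT to mean less pain.

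**The concern.** The visit list is what staff are likely to have in hand during the examination. Here it joins the name of one test to the positions of another and leaves the second test out. Depending on how the line is read, a centre could take mucosal readings at positions that Section 15.2 does not define for the mucosa, or take muscle readings and file them as mucosal.

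Local PPT is an Aim 1 secondary endpoint (IIa), and the plan needs mucosal and muscle thresholds as distinct outcomes. The distinction matters in this trial because the cream is applied to the vestibule (Section 8.1), so equal effects on mucosal and muscle thresholds cannot be assumed. A set not taken at baseline cannot be recovered for a change-from-baseline analysis.

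**Working it through.** The plan gives no numerical figure for the PPT endpoints (Section 15.6 does not mention them), so the check is a comparison of texts.

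| Source | Name | Clock positions | Access |
|---|---|---|---|
| Visit lists, 10.1 and 11.1 to 11.3 | vestibular | 5, 6, 7 | not stated |
| Section 15.2 | vestibule | 2, 10, 6 | external |
| Section 15.2 | levator | 5, 6, 7 | internal |
| Appendix A | vestibule; perineal muscle; levator (three rows) | none given | not stated |

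**Overlap.** {5, 6, 7} and {2, 6, 10} share only 6 o'clock, so 1 of 3 vestibule positions. {5, 6, 7} and {5, 6, 7} share 3 of 3 levator positions. Even the shared 6 o'clock is not the same reading, because one test reaches it externally and the other internally.

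**What each reading of the line would yield.**
- The label governs: mucosal readings at 5, 6 and 7 o'clock, of which 1 of 3 is a Section 15.2 vestibule position, and no levator set.
- The positions govern: a levator set stored under the vestibular name, and no vestibule set.
- Appendix A and Section 15.2 govern: both sets at every visit, with the visit-list line treated as a slip.

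Only the third supports the analyses in Section 15.2.

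**Could the levator test sit under another step?** The other pelvic steps in the lists are the qualitative sensory test and vaginal sampling. Appendix A gives each of these its own row, apart from the PPT rows. The levator test therefore has no place in the stated order.

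**Which text governs?** Sections 5.3, 5.4 and 10 point to Appendix A for the complete schedule, and Section 10.1 points to Section 15 for detail. Sections 11.1 to 11.3 carry no pointer to Section 15. No section says which text prevails in a conflict.

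**Mapping to endpoints.** Section 15.2 names mucosal and vulvovaginal muscle outcomes but does not tie them to Appendix A rows. It is not stated whether the muscle outcome uses the levator row, the perineal row or both.

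**If the two centres resolved the line differently.** This is a conditional illustration; nothing in the documents shows that it happens. Section 9.2 targets 200 women per centre, and 200/400 = 0.5. If one centre measured vestibule and the other levator under one name, the pooled effect would be about 0.5 × (vestibule effect) + 0.5 × (levator effect). The center term in the model removes a difference in mean level between centres, but not this mixture of effects.

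**The case against.** The strongest reply is that the visit lists are not the only instruction, nor a complete one. Appendix A schedules vestibule and levator PPTs separately at all four time points, and Section 15.2 gives positions and access route for each. The lists also leave out other things the plan requires: the two further pain ratings and medication compliance in Appendix A, and the adverse-event probing in Section 14.2.4. Section 5.1 sets up a feasibility study to standardise PPT measurement before screening starts, and Section 13 provides calibration and retraining. PPTs are secondary.

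Most of this stands, and it rules out several stronger conclusions that a reader might draw:

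- *That the vestibular and muscle endpoints cannot both be derived.* Appendix A with Section 15.2 provides for both at every visit.
- *That all 400 women are affected.* This assumes that every centre ignores Appendix A and Section 15, which nothing in the documents shows.
- *That the treatment comparison is confounded by centre.* Randomisation is stratified by site (Section 8.7) and center is in the model. Different techniques would blur what is measured, but would not bias the allocation.
- *That the perineal row should be deleted.* The sentence introducing the PPT endpoints in Section 15.2 breaks off in the available text, so a perineal method may have been lost in extraction. The muscle endpoint could also include that row.
- *That the direction wording could turn a worsening into a success.* It appears only in the expected-outcomes narrative, no decision rule uses it, and the planned intervals are two-sided.

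The reply does not remove the contradiction. An incomplete list can be supplemented from elsewhere, but this line gives positions that conflict with Section 15.2. Training can only calibrate staff to one site set once the protocol settles which one applies.

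**Conclusion.** The point holds as an internal inconsistency in an operative measurement instruction, repeated in all four visit lists. The listed positions match 3 of 3 levator and 1 of 3 vestibule positions under a vestibular label, and no levator step appears. Staff who work from the lists could collect only one of the two local sets, or mislabel it. That would degrade the mucosal and muscle PPT secondary endpoints and the three muscle-pain analyses.

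Severity is moderate. The tampon test and SF-MPQ primary endpoints and the sample size do not depend on these readings. Harm to the data depends on the assumption that at least some staff follow the lists over Appendix A and Section 15.2; the documents neither show nor exclude this. They also do not establish which site set was intended. The PPT direction wording is a separate, minor drafting error.

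**What to change.** 1. Reconcile Sections 10.1, 11.1 to 11.3, 15.2 and Appendix A, with the sponsor confirming the intended sites. Section 15.2 is the natural source, because Section 10.1 refers to Section 15 for detail.
2. In all four visit lists, give the vestibule and levator PPTs separate lines, each with clock positions, access route and place in the order. Use separate data fields.
3. State which Appendix A rows feed the mucosal and the vulvovaginal muscle endpoints. Say explicitly what the perineal row is for and how it is measured.
4. If data already exist, document which sites were measured at each centre, and from when, before any PPT analysis.
5. As a wording correction, state the expected benefit in Section 15.2 as an increase in PPT, consistent with Section 15.1.

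The cost is protocol wording and a check of the data fields. Both tests are already in Section 15.2 and Appendix A, so no procedure is added.

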10.2 Drug Dispensing

All eligible study participants who successfully complete screening and baseline evaluations will be randomized (as detailed in **Section 8.7**) to receive one of four types of medication kits:

- 5% lidocaine/0.5mg/ml 0.07% estradiol compound vaginal cream + placebo pill
- placebo vaginal cream + nortriptyline pill
- 5% lidocaine/0.5mg/ml 0.07% estradiol compound vaginal cream + nortriptyline pill
- placebo vaginal cream + placebo pill

Identical-appearing creams and pills will be packaged and distributed by the Central Compounding Pharmacy to UNC and by the Pacifica Compounding Pharmacy to UCLA. At the baseline visit, participants will receive a sufficient supply of study drug for weeks 1-8. Patients will be instructed to take the medication as required by the protocol and complete a daily medication calendar (**Appendix D**).

11 FOLLOW-UP EVALUATIONS

11.1 Visit 2 (8-Week)

Upon arrival, participants will return any remaining study medication to the research team.

The week 8 visit procedures and assessments will be performed in the following order:

- Tampon test with 0-10 NRS
- Blood collection and processing
- Participant questionnaires:

- VPAQ
- PROMIS BPSFS-F
- COPC follow-up survey
- SF12v2
- SCL-27
- PILL
- PSS
- Sleep scale
- Remote bodily PPTs (deltoid, shin, trapezius)
- Qualitative pelvic sensory testing
- Vaginal sample collection
- Local vestibular PPTs (5, 6, and 7 o'clock)

At the end of visit 2, participants will receive a sufficient supply of study drug for weeks 9-16. Patients will be instructed to take the medication as required by the protocol and complete a daily medication diary.

11.2 Visit 3 (16-Week)

Upon arrival, participants will return any remaining study medication to the research team. Study medication will be discontinued.

The week 16 visit procedures and assessments will be performed in the following order:

- Tampon test with 0-10 NRS
- Blood collection and processing
- Participant questionnaires:
 - VPAQ
 - PROMIS BPSFS-F
 - COPC follow-up survey
 - SF12v2
 - SCL-27
 - PILL
 - PSS
 - Sleep scale
- Remote bodily PPTs (deltoid, shin, trapezius)
- Qualitative pelvic sensory testing
- Vaginal sample collection
- Local vestibular PPTs (5, 6, and 7 o'clock)

11.3 Visit 4 (24-Week)

The week 24 visit procedures and assessments will be performed in the following order:

- Tampon test with 0-10 NRS
- Blood collection and processing
- Participant questionnaires:
 - VPAQ
 - PROMIS BPSFS-F
 - COPC follow-up survey
 - SF12v2
 - SCL-27
 - PILL
 - PSS
 - Sleep scale
- Remote bodily PPTs (deltoid, shin, trapezius)

- Qualitative pelvic sensory testing
- Vaginal sample collection
- Local vestibular PPTs (5, 6, and 7 o'clock)

